### **DATA ANALYSIS**

Digital data files will be stored in a protected limited-access folder on the MFA network. Only the Study Biostatistician and the PI will have direct access to the data once it is on this server. The data file will have random subject identifiers and will have no HIPAA identifiers.

The distributional assumptions of all measures will be examined. Means and standard deviations will be computed for continuous measures and proportions for categorical variables. Graphical representations of the mean group slopes and individual slopes will be generated and inspected.

Study groups will be compared to determine whether any imbalance between the groups on patient characteristics remain after randomization. If imbalance is evident, by inspection, all models will be adjusted for the unbalanced covariates. Change in outcome over time will be examined using a multilevel approach with linear mixed models (LMM). The longitudinal multilevel modeling approach will enable us to examine characteristics of within-person change, as well as between-group differences that may influence change. LMMs handle missing data more efficiently than traditional ANOVA designs. In the linear mixed models, the patient is considered a random effect and the outcome measured at specific time points is nested within patient. Time (week 0, 8, 16) will be modeled as a continuous variable in order to assess linear effects from 0 to 8 to 16 weeks. In order to determine whether there are non-linear time effects (e.g., rapid increase from 0 to 8 weeks followed by little change from 8 to 16 weeks; or initial decrease at 8 weeks followed by increase at 16 weeks, etc.) we will also need to include models in which time is defined as a class variable (with 0 as the reference group). Subsequent analyses will add study group and other patient characteristics as covariates. We are particularly interested in whether there is a significant interaction between study group and time, adjusting for other patient level covariates. A significant interaction would indicate that the slopes in outcome over time differ by study group. If the global test of interaction is significant, subsequent significance testing of the pair wise comparisons of group slopes group will be adjusted for multiple comparisons. The model also includes coefficients for the group-by-time interactions and random effects for patient and time.

$$Y_{ij} = \beta_0 + \beta_1 Time_{ij} + \beta_2 Group_i + \beta_3 (Time_{ij} \times Group_i) + \varepsilon_{ij}$$

The interaction between GROUP and TIME will be modeled in a similar fashion using two additional indicator variables. The above multivariable model enables us to adjust for time-varying covariates, such as glucose. Since glucose will be measured contemporaneously with the outcomes at each visit, however, causal interpretations of glucose and any outcome are suspect. As such, we will consider glucose as a nuisance covariate, and consider any relationship between glucose and an outcome as merely associative.

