# 2 STUDY OBJECTIVES

## PRIMARY OBJECTIVE

**To determine whether 4 months of Canagliflozin modifies CD34+ cell number, gene expression and migration function.**

## PROTOCOL FOR OBTAINING CD34+ CELLS:

We will obtain a total of approximately 95 mL of peripheral blood per visit. Of these 95 mL, 60-70 mL will be used to obtain CD34+ cells from mononuclear cell (MNC) population and 25-35 mL for biochemistry and plasma ELISA assays. MNC will be obtained from whole blood similar to protocols described before. MNCs will be put through CD34 magnetic bead column to obtain CD34+ cells (Miltenyi Biotec). Purity of CD34+ cells, post sort, usually is above 90%, to be verified by FACS analysis.

- A. From Mononuclear (MNC) population (pre CD34+ magnetic column sorting): We will assess the proportion of various cell types, progenitor stems and mature cells in MNCs to note if Cana influences stem vs non stem cell pool such as percentage of : CD34, CD309 (VEGFR2-KDR), CD184 (CXCR4), receptor substrate for SDF1 alpha, CD31 (PECAM-1, a mature circulating endothelial cell marker), CD133 (a progenitor marker), CD144 (Vascular Endothelial cadherin), Sytox Blue OR Propidium Iodide staining (to detect apoptotic cells).
- B. MNC cells (prior to CD34 magnetic bead sorting) will be also used to assay CFU Hill Colony forming unit (Stem Cell Technologies- Cat#05900) media for Colony Forming unit (CFU) Assay. CFU will be counted on 5-7 days post plating (from initial plating).
- C. From CD 34+ cell population (Post Sorting):
  - a. Migration Assay using SDF1Alpha concentrations of 0, 10, 100ng/ml and VEGF-A concentrations of 20 and 50 ng/ml, using 150,000 cells in 300ul serum free cell suspension media per insert.
  - b. Gene expression studies. Genes to be assessed on sorted CD34 positive cells:

- i. Endothelial lineage cell surface markers: CD34, VEGFR2 (KDR), CD31, CD144
- ii. For Anti-oxidant gene expression: Superoxide dismutase (SOD) 1, 2 and 3, catalase, glutathione- peroxidase.
- iii. Apoptosis pathway: p53, p21, Bcl2, caspase-3
- iv. Endothelial Function Assay Gene: endothelial Nitric Oxide Synthase, von-Willebrand's Factor
- v. Genes associated with progenitor cell chemotaxis: VEGF-A, SDF1 alpha, CXCR4.

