### **Study Design Overview:**

We propose a 2-arm randomized, double-masked, placebo-controlled, parallel group, longitudinal study of 16-weeks duration. (See study design below), recruited over 2 years. The 16 week time interval has been previously shown adequate to observe changes in endothelial progenitor stem cells, biochemistry and importantly, PWV changes. Patients will be randomized to 2 groups:

Control, (n=20), metformin, insulin or Combo + Placebo

Treatment, (n=20) metformin, insulin or Combo + Cana 100mg

This proposed study is based on patients with type 2 diabetes, who are on any combination of the following anti-diabetic therapies: metformin (1-2 grams), insulin, GLP-1 agonists, a DPP-IV inhibitor, or sulfonylureas but still remain poorly controlled with HbA1C between 7.0% and 10% (both inclusive), but not overtly out of control (> 10% of HbA1C).

Though our study is over 16 weeks we do not anticipate significant drop in HbA1C in between the two groups in this relatively short time period to act as a confounding factor on CD34+ cell number, function and gene expression.

Subjects will be taking 100 mg of Cana or placebo. Dose titration of metformin, will not be allowed. Dose titration of insulin will be allowed to avoid hypoglycemia while maintaining HbA1C under 10%.

Most clinical studies looking at HbA1C reduction were of a much longer duration of 6 months or above and most DPP-4 inhibitor studies are with animal EPCs where comparison with human CD34+ population is difficult to make. In one study where saxagliptin was used for 12 weeks

in drug-naïve type 2 diabetes patients there was placebo-subtracted HbA1c reduction noted of 0.45-0.63%. It showed mean placebo-subtracted reductions in fasting serum glucose of 20 mg/dL. From our laboratory studies of in vitro human EPC studies we do not think glucose level change of 20 mg/dL is significant enough to account for changes in EPC number, function and gene expression. However we will take the possibility of glycemia change/ reduction in experimental arm into account during statistical analysis of the results between the Canagliflozin and placebo groups.

*Visits with outcome measurements* will be scheduled for the morning while overnight fasting (except water) to reduce diurnal variability, and clinical parameters will be obtained at scheduled office visits as depicted in the study schema and will be measured at each outcome visit as follows:

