**To determine whether 4 months of Canagliflozin modifies CD34+ cell number, gene expression and function.**

Protocol for obtaining CD34+ cells: We will obtain a total of approximately 95 mL of peripheral blood per visit. Of these 95 mL, 60-70 mL will be used to obtain CD34+ cells from mononuclear cell (MNC) population and 25-35 mL for biochemistry and plasma ELISA assays. No samples will be stored for future research. MNC will be obtained from whole blood similar to protocols described before. MNCs will be put through CD34 magnetic bead column to obtain CD34+ cells (Miltenyi Biotec). Purity of CD34+ cells, post sort, usually is above 90%, to be verified by FACS analysis.

- A. From Mononuclear (MNC) population (pre CD34+ magnetic column sorting): MNC cells (prior to CD34 magnetic bead sorting) will be also used to assay CFU Hill Colony forming unit (Stem Cell Technologies- Cat#05900) media for Colony Forming unit (CFU) Assay. CFU will be counted on 5-7 days post plating (from initial plating).
- B. From CD 34+ cell population (Post Sorting):
  - a. Migration Assay using SDF1Alpha concentrations of 0, 10, 100ng/ml and VEGF-A concentrations of 20 and 50 ng/ml, using 150,000 cells in 300ul serum free cell suspension media per insert.

- b. Gene expression studies. Genes to be assessed on sorted CD34 positive cells:
  - i. Endothelial lineage cell surface markers: CD34, VEGFR2 (KDR), CD31, CD144
  - ii. For Anti-oxidant gene expression: Superoxide dismutase (SOD) 1, 2 and 3, catalase, glutathione- peroxidase.
  - iii. Apoptosis pathway: p53, p21, Bcl2, caspase-3
  - iv. Endothelial Function Assay Gene: endothelial Nitric Oxide Synthase, von-Willebrand's Factor
  - v. Genes associated with progenitor cell chemotaxis: VEGF-A, SDF1 alpha, CXCR4.

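### The plan does not say whether the main group-by-time test adjusts for glucose at weeks 8 and 16; if it does, the coefficient is not in general the total treatment effect in the primary objective

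*Combined protocol and SAP*

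**What the plan says.** The primary objective is worded twice, without any condition on glucose: in Section 2, "To determine whether 4 months of Canagliflozin modifies CD34+ cell number, gene expression and migration function", and again in the Primary Objective part of Section 6, "To determine whether 4 months of Canagliflozin modifies CD34+ cell number, gene expression and function".

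Section 7, Data Analysis, makes the interaction the test of interest: "We are particularly interested in whether there is a significant interaction between study group and time, adjusting for other patient level covariates". Those covariates are not listed. The modelling is staged: "Subsequent analyses will add study group and other patient characteristics as covariates". The equation then printed contains Time, Group, Time x Group and an error term only. The text below it adds "The above multivariable model enables us to adjust for time-varying covariates, such as glucose". It notes that glucose is measured at the same visits as the outcomes, and concludes "we will consider glucose as a nuisance covariate, and consider any relationship between glucose and an outcome as merely associative".

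Study Design Overview in Section 6 expects little between-group difference in HbA1c over 16 weeks and argues that a 20 mg/dL glucose change is too small to explain changes in the cells. It nevertheless says "we will take the possibility of glycemia change/ reduction in experimental arm into account during statistical analysis of the results". The method, the variable and the model are not given. The same section allows background insulin to move: "Dose titration of insulin will be allowed to avoid hypoglycemia while maintaining HbA1C under 10" percent.

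The Synopsis lists fasting glucose and HbA1c among the secondary outcomes. The Synopsis hypothesis and Section 1 also propose a benefit that does not depend on better glycaemic control, which is a separate question from the primary objective.

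**The concern.** Assignment to canagliflozin or placebo is randomised; glucose at weeks 8 and 16 is not. It comes after randomisation, the Introduction describes the drug class as improving glycaemic control, and it can also respond to insulin titration during the trial. The Introduction reports that high glucose harms CD34+ cells, so a path from drug to glucose to cells is at least possible.

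Putting such a variable in the model can do two things to the group-by-time coefficient. It can remove whatever part of the effect runs through glucose. It can also bring in bias from unmeasured causes that glucose and the cell outcomes share. The plan's caveat that the glucose-outcome relationship is only associative does not cover either of these, because both concern the treatment coefficient.

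Two analysts following this text could fit different models, get different answers, and each claim to have followed the plan. The choice should be closed before unblinding. The unblinding procedure lets clinical measures be unblinded while analysis of the cellular data lags behind. If glucose counts as a clinical measure, its difference between arms could be known before the CD34+ model is chosen.

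**Working it through.** **Reading the passages together**

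1. Estimand: the primary objective asks what assignment to the drug does to the CD34+ outcomes. This is a total effect.
2. Test: group-by-time interaction, adjusted for unlisted patient-level covariates.
3. Printed model: no glucose term.
4. Text on glucose: one permissive statement (the model allows adjustment) and two commitments (glucose treated as a nuisance covariate; glycaemic change taken into account).
5. Missing link: nothing says whether points 2 and 4 are the same model or different ones.

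**Size, as an illustration**

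The plan gives no figure for the effect of adjustment, so there is none to reproduce. From the documents come 16 completers per arm (16 / (1 - 0.20) = 20 randomised per arm, which agrees with the plan), visits at weeks 0, 8 and 16, and the 20 mg/dL figure, which Study Design Overview takes from a saxagliptin study and not from canagliflozin. Everything else is assumed: glucose SD 40 mg/dL, within-patient correlation 0.6, a glucose fall growing linearly to 20 mg/dL at week 16, outcome SD held at 1, and a glucose-outcome slope between 0 and 0.01 SD per mg/dL.

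Expected shift in the week-16 coefficient after adjustment = slope x 20:
- 0.005 x 20 = 0.10 SD (correlation 0.005 x 40 = 0.2)
- 0.01 x 20 = 0.20 SD (correlation 0.01 x 40 = 0.4)

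*Mediation.* The true total effect is 1.0 SD, part of it acting through glucose. The random-intercept model used 4,000 simulated trials per row.

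| Slope | Estimate unadjusted | Estimate adjusted | Power unadjusted | Power adjusted |
|---|---|---|---|---|
| 0 | 1.01 | 1.01 | 88.0% | 86.6% |
| 0.005 | 1.01 | 0.91 | 87.9% | 81.1% |
| 0.01 | 1.00 | 0.80 | 87.0% | 75.5% |

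With random effects for patient and time, as the Data Analysis text asks (3,000 trials), the adjusted estimates are 0.99, 0.90 and 0.80. Power is 82.9%, 75.8% and 73.1% adjusted, against 84.0%, 84.0% and 85.1% unadjusted.

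*Confounding.* Neither drug nor glucose affects the outcome, but an unmeasured common cause links glucose and outcome at each visit (random intercept, 3,000 trials).

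| Correlation (absolute) | Estimate unadjusted | Estimate adjusted | Type I error unadjusted | Type I error adjusted |
|---|---|---|---|---|
| 0.2 | -0.01 | -0.11 | 5.5% | 6.8% |
| 0.4 | 0.01 | -0.20 | 4.9% | 9.2% |

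The simulation error of the 5.5% is about sqrt(0.055 x 0.945 / 3000) = 0.4 percentage points, so the first row shows only a small gap. The bias changes sign if the common cause moves glucose and outcome in the same direction.

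**Limiting cases**

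A separate large-sample simulation used other assumed values: glucose SDs of 30 between and 25 within patients, and a 20 mg/dL fall. With a total effect of 0.4 acting wholly through glucose, the coefficient is 0.41 unadjusted and 0.01 adjusted. With a total of 0.4 and none of it through glucose, both models give 0.40. Adjustment is thus harmless when glucose plays no part and can remove the whole effect when glucose carries it.

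**The case against.** The best reply is that the text already points to a glucose-free main model. In a multilevel framework, patient-level covariates normally have one value per patient. The plan puts glucose in a different class, time-varying, and says only that the model permits adjustment. The one printed equation omits it. This reading is reasonable, and it defeats the stronger inference a reader might draw, that the plan commits to a glucose-adjusted primary test and so to a biased one. It does not close the point: no model is named as primary, and the two statements of intent on glucose are commitments, not options.

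Second, adjustment serves a stated hypothesis, benefit beyond glucose control. That stands. It is a reason to keep the adjusted model as a planned secondary analysis, not to strike it out.

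Third, the plan expects little glycaemic difference, so the gap may be nil. That also stands as to size. A reader might infer that the Introduction's remark on glucose toxicity contradicts the 20 mg/dL argument. It does not: the remark gives no threshold and says nothing about a change of that size, and the mechanism proposed there is reduced glucose entry into the cell, a direct drug action. Toxicity makes mediation possible and no more. Equally, an expected small difference does not tell the analyst which model to fit.

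**Conclusion.** The concern holds as an unresolved choice of model. The plan leaves open whether week 8 and 16 glucose enters the group-by-time test, and its wording leans towards including it. If included, the coefficient is in general not the total effect in the primary objective. The two coincide only when treatment does not change glucose, or when glucose is unrelated to the outcome given treatment and shares no unmeasured cause with it. Nor does the adjusted coefficient by itself establish an effect independent of HbA1c, as Section 1 proposes; that needs an assumption of no unmeasured confounding between glucose and outcome.

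The documents do not fix the size, and it may be zero. On the assumed inputs the shift is 0 to 0.20 SD. Part of the power difference in the mediation case simply reflects that the adjusted model tests a smaller quantity. These figures do not show that the trial's error rate is inflated; they show that the choice can matter. The conclusion rests on the text and on the timing of the glucose measurements, not on the simulations. It should be corrected, since only the model free of post-randomisation covariates has the protection of randomisation.

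**What to change.** In Data Analysis, below the equation, state that the primary group-by-time test includes no covariate measured after randomisation, and specifically no week 8 or 16 glucose or HbA1c. State in advance whether baseline HbA1c or glucose is included, as a fixed yes or no. Say that patient-level covariates means baseline values, including any added for imbalance. So that the sentence points to one model, name the coding of time it uses (the section has both continuous and categorical time) and show the random effects that the equation omits.

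Keep the time-varying-glucose model as a labelled secondary analysis of the hypothesis in the Synopsis and Section 1. State its no-unmeasured-confounding assumption, and do not use it alone to claim independence from glycaemia. Point the sentence in Study Design Overview to that analysis.

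The cost is about one paragraph and one cross-reference, with no new data; the glucose-free model is already printed. The price is that the glucose-independence question is answered only by a secondary analysis that depends on an untestable assumption.

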### **Privacy Protection**

All data collected for the research study will be collected under a random subject ID.

- All samples being sent to LabCorp for standard of care labs will be labeled with the subject ID, DOB, Date of visit, time of collection, and Visit number. These samples will not be stored as they will be sent down to LabCorp immediately.
- The whole blood and plasma being used for ELISA and CD34+ analysis will be labeled with the subject ID, Date of visit, and Visit number. No additional data will be provided with the samples. These samples will be analyzed and stored at The George Washington University Ross Hall in [name],
- The urine sample being used for the exosome sub-study will be labeled with the subject ID, Date of visit, time of collection, and Visit number. They will also be provided with subject gender, and age. These samples will be analyzed and stored (as per the protocol below) at the VA by [name].

All other study data will be both electronically stored on a secure server, and physically stored as patients files locked in the Department of Medicine. The only individuals who will have access

to the study data will be the members of the research staff team, as indicated in the GW IRB Form “Research Team Personnel Form (HRP-201)”.

## **8. APPENDIX A: OPTIONAL URINE EXOSOME STUDY, Veterans Affairs, [name]**

A urine sample is already required as a part of [name] protocol. This urine will be used for urine pregnancy tests (if applicable), and labcorp tests for microalbumin/creatinine ratio. There will be excess urine.

Subjects will have the option to opt in or out of a research study being conducted by [name] of the VA, in which the urine will undergo a urine exosome analysis.

**Purpose of this Study:** Exosomes are cell-derived vesicles that are present in many and perhaps all biological fluids, including blood, urine, and cultured medium of cell cultures. The reported diameter of exosomes is between 30 and 100 nm, which is larger than LDL, but much smaller than for example, red blood cells. Exosomes are either released from the cell when multivesicular bodies fuse with the plasma membrane or they are released directly from the plasma membrane. Evidence is accumulating that exosomes have specialized functions and play a key role in, for example, coagulation, intercellular signaling, and waste management. Consequently, there is a growing interest in the clinical applications of exosomes. Exosomes can potentially be used for prognosis, therapy, and biomarkers for health and disease. In this study we are particularly interested in exosomes released from podocytes as a marker of podocyte function and podocyte inflammation. Podocytes are often considered a modified endothelium and one of its more commonly used parameter is microalbuminuria. In this study we are using urine exosomes as an added parameter of kidney function other than microalbuminuria and GFR calculation.

### **The procedure for this study is as follows:**

10-50 mL of the fresh spot urine is placed into a urine cup containing 1 tab of cOmplete Ultra - protease inhibitor cocktail (Roche) for exosome analysis performed at the Veterans Affairs (VA) Maryland Health Care System.

The specimen can be refrigerated at 4°C for ~ 1 week, frozen at -80C, or processed immediately. Transfer to the VA will be done following appropriate procedures outlined in the MFA-VA Materials Transfer Agreement (MTA). The urine will be processed for exosomes as follows:

The supernatant may be subjected to ultracentrifugation, with final centrifugation at 200,000g for 2 hr at 4°C to obtain the urinary exosome pellet. The pellet would then be tested for exosomes markers, namely CD63, CD9, CD81, Hsp70, and WT-1, nephrin and podocalyxin, using one of two methods. Preferably mRNA will be extracted and then RT-PCR will be run. Alternative analysis will be done using gel electrophoresis followed by Western blot techniques.

### **Method 1: Urine exosome mRNA extraction**

mRNA extraction from exosomes will be accomplished by using commercial kits (Norgen Biotek Corp., Catalog # 47200). Thereafter, a pre-amplification step will take place, this is a

necessary step to measure mRNA in exosomes and will be followed by quantification of specific endothelium and podocyte proteins such as CD9, WT-1, nephrin and podocalyxin by RT-PCR.

Total urinary protein content, albumin and creatinine will be measured via Lapcorp for the same urine samples that have been collected.

